#### Objective 6:

The impact of the restrictions of use will be estimated using an ITS. This analysis will be restricted to NOMAC and CMA (assessed separately) and will be informed by results of the main analysis obtained as part of objective 1 (no meningioma restriction). For NOMAC, the intervention taken place in 2018 will also be assessed.

Time series will be assessed using segmented regression. Monthly incident counts of patients prescribed with NOMAC or CMA will be modelled using a Poisson regression model. Quasi-Poisson models will be considered in the presence of overdispersion. The effect size of the intervention will be estimated using risk ratios (RR).

The assumption of linearity will be assessed by visually inspecting the data and residuals, as well as through statistical goodness-of-fit tests. Autocorrelation will be assessed by examining the plot of residuals and the partial autocorrelation function and conducting statistical tests where possible. If seasonality is detected, it will be controlled for by including variables representing them in the regression model. If the trends are not (or cannot be transformed to be linear) or in the presence of residual autocorrelation, ITS will not be conducted due to the complexity of predicting the counterfactual and to disentangle the intervention effects.(23)

Authors: [name], [name], [name], [name], [name]

Version: V4.0

Dissemination level: Public

The impact model of the intervention (i.e. how we expect the intervention has impacted the outcome) is anticipated to show an abrupt change in the level and a gradual change in the gradient of the trend (step and slope change). Potential impact models will be further discussed and agreed with EMA and defined a priori.(23, 24)

The amount of pre-intervention data to include for this analysis will be based on defining a valid counterfactual for the ITS analysis. Given the large amount data (12 years before the intervention), the range of pre-intervention data will be restricted to ensure the validity of the comparison (i.e. historical trends might differ from the most recent ones). To analyse the impact of restrictions adopted in 2022, analysis will be conducted using data from 1st January 2021 onwards. For NOMAC, the intervention adopted in 2018 will be assessed using data from 1st January 2017 onwards. Methodological considerations will be evaluated based on the visual assessment of the trends. This may include adjustments on the amount of pre-intervention data or the frequency of data points, if deemed necessary to support the analysis.

Results will be reported overall and stratified by dose (high- vs. low- dose products) and indication (non-HRT vs. HRT).

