#### 6. RATIONALE AND BACKGROUND

Medicines containing nomegestrol acetate (NOMAC) or chlormadinone acetate (CMA) are synthetic progestins with antiandrogenic effects. Approved indications for NOMAC and CMA in monotherapy or in combination with oestrogens differ between different strengths and different countries. In general, they are indicated for gynaecological and menstrual disorders, hormone replacement therapy (HRT) and, at lower doses, as hormonal contraception.

Meningioma is a rare tumour that forms from the meninges. Known risk factors for meningioma are being female, exposure to ionising radiation and neurofibromatosis type 2.(1) Recently published studies have found a dose-dependent association between NOMAC or CMA and meningioma.(2-5) The hazard ratio (HR) of intracranial meningioma adjusted for age was 4.5 (3.5-5.7) and 4.4 (95% CI 3.4-5.8) among women exposed to NOMAC and CMA, respectively.(2, 3) The risk of meningioma increased with dose and duration of treatment and diminished one year after the discontinuation of treatment. Prolonged exposure to progestogens other than NOMAC such as cyproterone acetate (6) and medroxyprogesterone acetate (7) has also been linked to an increased risk of meningioma.

The risk of meningioma associated with NOMAC is known since 2018 and has been assessed within different regulatory procedures.(8) In October 2018, the Pharmacovigilance Risk Assessment Committee (PRAC) recommended to amend the product information of monotherapy products containing NOMAC to include the contraindication for patients who have, or have had, meningioma. PRAC also recommended permanently discontinuing treatment in patients who develop meningioma. In 2020, the product information of products containing NOMAC in combination with oestradiol was updated with similar contraindications and warnings.

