#### **Covariates for stratification:**

Covariates for stratification will vary across objectives and will include:

- Age group:
   10-17, 18-34, 35-49, 50-64, +65 years.
- Indication:

Non-HRT vs. HRT. Indication will be assessed using age as a proxy (non-HRT in women aged 10-49 years, HRT in women aged >50 years).

- Dose:
  - High- vs low- dose, for NOMAC or CMA only. For NOMAC, high doses will include amounts from 3.75mg to 5mg. For CMA, high doses will include amounts from 5mg to 10mg. Low doses will be any amounts less than those specified.
- WHO 5th ATC level codes:
  - For NOMAC or CMA only, if counts allow. For NOMAC codes included will be: G03AA14, G03DB04, G03FB12. For CMA, codes included will be: G03AA15, G03AB07, G03DB06, G03FB03.
- Time period:
  - Preintervention: from start date to October 2022; Postintervention: from February 2023 to study end.

See below which covariates apply according to each objective.

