	Objective 4: Study population, study period, exposure of interest (NOMAC vs. CMA), dose and indication.
	Objective 5: Study population, WHO ATC 5th level (if counts allow), study period, dose.
	Objective 6: Dose (high-dose products only), indication.

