# **Drug classes:**

Drug class	Analysis	WHO ATC 4 th level codes 	WHO ATC 5 th level codes 
Progestogens that are pregnadien derivates	Objective 1	G03DB	All descendants included
Progestogen and oestrogen combination products	Objective 1	G03AA, G03AB, G03FA, G03FB	All descendants included

Authors: [name], [name], [name], [name], [name]

Version: V4.0

Dissemination level: Public

		T .	I
Medroxyprogesterone 	Objective 1	N/A	G03AC06, G03DA02,
			G03AA17, G03FA12,
			G03FB06, G03AA08,
			L02AB02
Nomegestrol	Objective 1 and 6	N/A	G03AA14, G03DB04,
			G03FB12
Chloramidinone	Objective 1 and 6	N/A	G03AA15, G03AB07,
	-		G03DB06, G03FB03
Progestogen and estrogen	Objective 4 and 5	G03AA, G03AB,	All descendants
combination products not	-	G03FA, G03FB	included, except:
containing nomegestrol or			G03AA14, G03AA15,
chlormadinone.			G03AB07, G03FB12 and
			G03FB03
Progestogens that are	Objective 4 and 5	G03DB	All descendants
pregnadien derivates not			included, except:
containing nomegestrol or			G03DB04 and G03DB06.
chlormadinone.			
Drug classes of interest (any)	Objective 3	G03AA, G03AB,	All descendants
		G03DB, G03FA, G03FB	included

<sup>1 All descendants included.

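### The overall 2018 interrupted time series pools monotherapy and combination NOMAC, although the 2018 action covered monotherapy only, and no Objective 6 stratum is documented to separate them

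*Protocol*

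**What the plan says.** **Scope of the regulatory actions.** In Section 6, the October 2018 recommendation was to "amend the product information of monotherapy products containing NOMAC", adding a contraindication for women with current or past meningioma and calling for permanent discontinuation if meningioma develops. The same section continues: "In 2020, the product information of products containing NOMAC in combination with oestradiol was updated with similar contraindications and warnings".

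**Series analysed.** Section 8.8 (Objective 6) states: "For NOMAC, the intervention taken place in 2018 will also be assessed". It does not limit this to monotherapy. Section 8.6.3 gives the definition: "For NOMAC codes included will be: G03AA14, G03DB04, G03FB12". Appendix I lists G03AA14 and G03FB12 among the codes removed from the progestogen-oestrogen combination class, and G03DB04 among those removed from the pregnadien class. G03DB04 is therefore the monotherapy code.

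**Strata.** Sections 8.6.3 and 8.8 give Objective 6 two stratifiers, dose (high versus low) and indication. Table 11 differs: "Objective 6: Dose (high-dose products only), indication". ATC 5th-level stratification is planned for Objectives 1 and 5 only.

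**Window.** Section 8.8 starts the 2018 series on 1 January 2017 and gives no end date. Section 11 leaves the 2020 combination action out of the study because of the pandemic.

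**The concern.** An ITS attributes a break in a series to an intervention. Here the overall series contains products that the intervention, as the protocol describes it, did not address. If those products carried on as before, the break in the targeted products is averaged with no break elsewhere and the estimated RR moves towards 1. A reader could then take a diluted estimate as evidence that the 2018 measure had little effect.

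The reverse is also possible. If prescribing moved from monotherapy to combinations, the pooled series could show no change, or an increase, while monotherapy fell. The pooled RR cannot tell these situations apart.

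The mismatch does not depend on a later analysis plan, because the protocol itself fixes the substance definition and the Objective 6 strata. The flexibility it keeps for Objective 6 concerns the impact model, the amount of pre-intervention data and the spacing of data points, not which products form the series.

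**Working it through.** The protocol states no effect size, power or sample size for the 2018 ITS, so there is no figure to reproduce. The check sets scope against series, then works out what pooling does.

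**1. Scope against series**

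| Element | Monotherapy (G03DB04) | Combinations (G03AA14, G03FB12) |
|---|---|---|
| Covered by the 2018 action (Section 6) | yes | no, updated in 2020 |
| In the 2018 ITS series (Sections 8.6.3, 8.8) | yes | yes |
| Own ATC stratum in Objective 6 | no | no |
| Own ATC series in Objective 1 | yes, if counts allow | yes, if counts allow |

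**2. Can the dose strata stand in?** High-dose NOMAC is defined as 3.75 to 5 mg. Section 6 places contraceptive use at lower doses, so the low-dose stratum should take up at least some combination use. But the protocol gives no strength for the combinations and never equates high dose with monotherapy. Table 11 also drops the low-dose stratum that Section 8.8 keeps. The split is a partial proxy that the protocol does not document.

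**3. Dilution.** Let s be the monotherapy share of new NOMAC prescribing before the action, and RR the true ratio in monotherapy. Both are assumptions; the documents give neither. With combinations unchanged:

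pooled RR = s x RR + (1 - s) x 1 = 1 - s x (1 - RR)

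| Assumed RR in monotherapy | s = 25% | s = 50% | s = 75% | s = 90% |
|---|---|---|---|---|
| 0.50 | 0.875 | 0.75 | 0.625 | 0.55 |
| 0.70 | 0.925 | 0.85 | 0.775 | 0.73 |
| 0.80 | 0.95 | 0.90 | 0.85 | 0.82 |

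For example, with RR 0.70 and s = 50%: 1 - 0.50 x 0.30 = 0.85. For a modest effect, RR 0.95 and s = 50%: 1 - 0.50 x 0.05 = 0.975, a shift of only 0.025.

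**4. Switching.** If combination use changes by a factor g, pooled RR = s x RR + (1 - s) x g. With RR 0.70 and an assumed g of 1.3:

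- s = 25%: 0.175 + 0.975 = 1.15
- s = 50%: 0.35 + 0.65 = 1.00
- s = 75%: 0.525 + 0.325 = 0.85

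**5. Does splitting cost more than it gains?** An illustrative Wald test of the step term was worked out for a segmented Poisson model with intercept, trend, step and slope change, at two-sided 0.05. It uses 21 pre-months (January 2017 to September 2018), drops 4 transition months, and uses 11 post-months (February to December 2019, an assumed end before the 2020 action). RR in monotherapy is 0.70, combinations are unchanged, and there is no overdispersion.

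| Assumed NOMAC initiators per month | Series | s = 25% | s = 50% | s = 75% |
|---|---|---|---|---|
| 100 | pooled | 16% | 49% | 84% |
| 100 | monotherapy only | 52% | 81% | 93% |
| 20 | pooled | 6% | 14% | 26% |
| 20 | monotherapy only | 14% | 24% | 34% |

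In these scenarios the monotherapy series has more power despite its smaller counts. At 20 initiators per month neither series is informative.

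**6. Rough counts.** Table 3 gives 1.9k NOMAC users in NAJS and 6.7k in Belgium, for the whole database without restriction. Spread evenly over the usable years in Section 11, that is about 1,900 / 82 = 23 persons per month (January 2017 to October 2023) and 6,700 / 144 = 47 persons per month (2012 to 2023), before any split.

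**The case against.** Several counter-arguments have force.

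- **The pooled RR answers the stated objective.** Objective 6 concerns products containing NOMAC, and a substance-level ratio is a legitimate quantity. This stands as a reason to keep the pooled result, but not to present it without saying that it includes products outside the 2018 action.
- **A large effect is not to be expected.** As Section 6 describes it, the 2018 measure was a contraindication and a discontinuation rule tied to meningioma, which the protocol calls rare. The restrictions on dose, duration and first-line use came in 2022. A reader might infer from the table that a large effect would be hidden. The documents do not support that: ratios of 0.50 or 0.70 are illustrations, and for a modest effect the dilution is small.
- **The separate series are already planned.** A reader might infer that the plan throws the comparison away. It does not: Objective 1 produces monthly incidence by ATC 5th-level code where counts allow. Only the modelling of those series is absent.
- **Combinations are not a clean control.** They contain the same active substance, so prescribers may have reacted across all NOMAC or moved women to combinations. With g = 1.3, dividing by that series would turn 0.70 into 0.70 / 1.3 = 0.54. With an assumed spillover of 0.9 it would give 0.70 / 0.9 = 0.78. This stands, so the combination series should be descriptive only.
- **Counts may not allow the split.** NAJS and Belgium are small, and cells below 5 are suppressed. If history before 2017 does not count in NAJS, the 365-day requirement leaves about nine pre-intervention months there (January to September 2018). This stands and makes the fix conditional on counts.

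**Conclusion.** The mismatch is real on the protocol's own text. The overall 2018 ITS pools targeted and non-targeted NOMAC products, and no Objective 6 stratum is documented to separate them. The dose split is a partial proxy on which Section 8.8 and Table 11 disagree. If combinations were unaffected, the pooled RR lies closer to 1 than the RR in monotherapy.

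The size cannot be fixed from the documents, because neither the monotherapy share nor the true effect is given. At the assumed RR of 0.70 the dilution ranges from substantial (0.925 at a 25% share) to slight (0.73 at 90%). The direction itself depends on combinations being unaffected; with switching the pooled RR could reach or exceed 1.

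This does not invalidate Objective 6, and it has no bearing on the 2022 analysis. It is a cheap improvement to how the 2018 result is targeted and read.

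**What to change.** In Section 8.8, Objective 6, for the 2018 intervention only:

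1. Run the ITS on G03DB04 as the targeted series in each database where counts allow.
2. Show G03AA14 and G03FB12 alongside, ending before the 2020 update, as a descriptive comparison. State that spillover or switching may affect it and that it is not a clean control.
3. Keep the pooled NOMAC result, with a sentence saying that it includes products the 2018 action did not cover.
4. Reconcile the dose strata between Section 8.8 (high versus low) and Table 11 (high-dose only).

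The inputs are already planned under Objective 1, so the cost is wording and the additional ATC-level series. The statistical price is smaller monthly counts and wider intervals. The split may prove infeasible in NAJS or Belgium; there, the pooled result with the statement in item 3 is what remains.

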	
 
Progestogens that are pregnadien derivates (including medroxyprogesterone and medroxyprogesterone alone)
 

	- Progestogen and oestrogen combination products.
	Objective 4: Same as Objective 2.
	Objective 5: Same as Objective 2.
	Objective 6: N/A
Comparator:	Before vs. After the implementation of restrictions
Outcome:	Objective 1: Prescribing of drug classes of interest (assessed separately)
	Objective 2: N/A (treatment duration and cumulative use of the exposure).
	Objective 3: N/A (characterisation of users)
	Objective 4: Prescribing of alternative treatments not containing NOMAC or CMA (assessed retrospectively to identify line of treatment).
	Objective 5: Number of patients diagnosed with meningioma during treatment and number of patients discontinuing treatment or switching to alternative treatments not containing NOMAC or CMA 180 days after the end of the index treatment.
	Objective 6: Prescribing of products containing NOMAC or CMA (assessed separately).
Time:	01/01/2010 to end of data availability
Setting:	Routinely collected data from 3 databases in 3 European countries.
Main measure of effect:	Objective 1:
	Incidence rates (new prescriptions per 100,000 person-years of the population at risk) and prevalence (proportions).
	Objective 2 to 5:
	- Objective 2: Median with minimum, maximum and interquartile range.
	- Objective 3-5: Counts and proportions
	
 
All objectives: Standardised Mean Differences (SMD) for comparing changes before and after the implementation of restrictions.
 

	Objective 6:
	Risk ratios derived from the interrupted time series analysis (ITS). ITS will be based on results obtained as part of Objective 1.

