#### A. Primary analysis

Hypothesis:	Objective 1: Not applicable, descriptive analysis.
	Objective 2: Cumulative dose and duration of treatments with NOMAC or CMA will be lower after the implementation of restrictions.
	Objective 3: The number of new users of NOMAC or CMA with prior history of meningioma will be reduced after the implementation of restrictions.
	Objective 4: The number of users initiating NOMAC or CMA as first-line treatment will be reduced after the implementation of restrictions.
	Objective 5: The number of discontinuations and switches from NOMAC or CMA to other drug classes will increase after the implementation of restrictions.
	Objective 6: The incidence of NOMAC or CMA will be reduced after the implementation of restrictions, especially for high-dose products. This reduction will not be observed for other drug classes of interest.
Exposure contrast:	Objective 1: Not applicable, descriptive analysis.
	Objective 2: Pre-intervention (1-year period) vs. Post-intervention (1-year period)
	Objective 3 to 6: Pre-intervention vs. Post-intervention
Outcome:	Objective 1: Incidence rates and prevalence of drug classes of interest
	Objective 2: Cumulative dose and treatment duration of NOMAC or CMA.

Authors: [name], [name], [name], [name], [name]

Version: V4.0

Dissemination level: Public

	Objective 3: Number and characteristics of users of drug classes of interest.
	Objective 4: Line of treatment when initiating NOMAC or CMA.
	Objective 5: Diagnosis with meningioma during treatment. Discontinuations and switches
	from treatments with NOMAC or CMA to others.
	Objective 6: Incidence rates of NOMAC or CMA.
	Drug classes of interest, NOMAC and CMA will be assessed separately.
Analytic software:	R
Model(s):	Objective 1: Not applicable, descriptive analysis.
	Objective 2 to 5: Standardised mean differences.
	Objective 6: Segmented regression (Poisson models).
Confounding adjustment method	
	Stratification.
Missing data methods	
	The absence of a record for a condition or medication will be considered as the absence of the disease or use of the medication.
Subgroup Analyses	
	Objective 1: Age groups, indication, study period. For NOMAC or CMA only: dose, WHO ATC 5 th level (if counts allow). A subgroup analysis will be performed restricting the study population to individuals with a prior history of meningioma.
	Objective 2: Study population, indication, study period.
	Objective 3: Study period.

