#### **Databases:**

In IQVIA LPD Belgium and IQVIA DA Germany, the observation period of the patients in these databases is calculated based on the last visit, observation or interaction of the patient with the health care system. This methodology impacts the individuals considered "at risk" for the different medicines of interest of the study (i.e., the individuals included in the denominator populations) during the latest months of available data from the latest data lock, where healthy and/or non-frequent users of the health care system will not be considered active. Consequently, the denominators that will be used to calculate the incident use of drugs in the population may present an artefactual decrease whilst the incident users will remain, incrementing the incidence and prevalence ratios. The presence of these artefacts will be considered when interpreting the results. However, this is likely to affect the amount of follow up available for the study. We expect that the data from the last 6 months may not accurately reflect actual figures of use and, therefore, will be excluded from the analysis for Objective 1 and 6.

Regarding the study period, NAJS will provide data from 2017 onwards only, as prior data might include information on duplicated patients. IQVIA LPD Belgium will provide data from 2012 onwards.

Since information on drug exposure end dates is unavailable in NAJS, treatment duration will not be inferred directly from the start and end dates of drug exposure. Instead, we will infer the treatment period using only the drug exposure start dates, assuming continuous drug exposure between consecutive start dates, if separated by less than 90 days. To account for the final prescription, we apply a 30-day window following the last recorded drug start date. This approach might lead to some uncertainty regarding the exact duration or cumulative dose prescribed.

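### Objective 6 models monthly counts with no stated denominator but names incidence rates as its outcome; fitted as written, the 2022 analysis can show February's length as an effect of the restrictions

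*Protocol*

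**What the plan says.** Section 8.8, Objective 6, fixes the modelled quantity: "Monthly incident counts of patients prescribed with NOMAC or CMA will be modelled using a Poisson regression model". For extra variation it adds: "Quasi-Poisson models will be considered in the presence of overdispersion". The effect is to be expressed as a risk ratio, here and in Table 1. The section covers linearity, autocorrelation, seasonality (modelled only if detected) and the expected step and slope change. It does not mention an offset, person-time or any other denominator.

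Table 11 names a different quantity as the outcome: "Objective 6: Incidence rates of NOMAC or CMA". Its hypothesis also concerns incidence: "Objective 6: The incidence of NOMAC or CMA will be reduced after the implementation of restrictions, especially for high-dose products". Table 1 lists only prescribing of the products as the Objective 6 outcome, and adds: "ITS will be based on results obtained as part of Objective 1". Objective 1 produces monthly rates per 100,000 person-years, so it yields both the counts and the person-time.

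**The concern.** A log-linear model of counts without an exposure term estimates how the number of new users changed. It equals a rate ratio only if the person-time behind each month is constant. Person-time is not constant, because months differ in length and the population at risk can change.

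Month length matters here because of the calendar. November 2022 to January 2023 are dropped as transition months, so each post series for the 2022 restrictions opens with the shortest month of the year. Where few post months follow, that low first point weighs heavily on the estimated level, and the following 31-day month shows up as a rising slope. The false drop is in the direction the protocol expects.

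Objective 6 is the only objective for which Table 11 specifies a regression model, so a false step of several percent bears on the study's one modelled estimate of impact.

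**Working it through.** The protocol gives no expected count, power or effect size for this model, so there is no figure of its own to reproduce. The check asks what the model in section 8.8 returns when nothing has changed.

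**Inputs**
- Series start: January 2021 (section 8.8). Transition: November 2022 to January 2023 (section 8.6.3). This leaves 22 pre-intervention months, January 2021 to October 2022, totalling 669 days, a mean of 669/22 = 30.41.
- Germany: data lock 30-09-2023 (Table 3), less six months (section 11), ends March 2023: 2 post months.
- Belgium: lock 31-12-2023, less six months, ends June 2023: 5 post months.
- Croatia (NAJS): lock 17-11-2023, last complete month October 2023: 9 post months. The six-month exclusion is written in the paragraph on the IQVIA sources. If it also covered NAJS, the series would end in April 2023, with 3 post months.

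**Model.** log E(count) = b0 + b1·time + b2·post + b3·(months since February 2023), Poisson. The level ratio is exp(b2), read at February 2023; the slope ratio is exp(b3). Expected counts are set proportional to days in the month, with a constant daily rate and population, so both true ratios are 1.

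**By hand for Germany.** The pre-intervention line extrapolates to 30.68 days in February 2023, with a trend of 1.0006 per month. Two post points are fitted exactly:
- level = 28/30.68 = 0.913
- slope = (31/28)/1.0006 = 1.106 per month

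**All sources, month length only**

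| Source (post months) | Level ratio | Slope ratio | Level ratio with one annual sine/cosine pair |
|---|---|---|---|
| Germany (2) | 0.913 | 1.106 | 0.932 |
| Belgium (5) | 0.952 | 1.013 | 0.971 |
| NAJS (9) | 0.965 | 1.005 | 0.979 |
| NAJS (3) | 0.935 | 1.034 | 0.954 |

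**2018 analysis of nomegestrol.** With January 2017 to September 2018 as the pre-period (21 months), February 2019 as the first post month and an assumed end in December 2020 (23 months), the level ratio is 0.986 and the slope ratio 1.000.

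**Change in the true population at risk.** The protocol gives no figure, so these are assumptions.
- A steady fall of 1% per month throughout gives level ratios of 0.913, 0.951 and 0.964 (Germany, Belgium, NAJS with 9 months). These are essentially the month-length values, because the baseline trend absorbs a steady drift.
- A fall of 1% per month that sets in after November 2022, with counts falling in step, means three monthly falls by February: 0.913 × 0.99³ = 0.886 for Germany. The fits for Belgium and NAJS give 0.923 and 0.936.
- With log person-time as an offset, that same scenario returns 1.000 for both level and slope in every source.

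**Denominator artefact in section 11.** Suppose the recorded denominators fall 2% per month while the counts stay correct. The counts are then unaffected. With the person-time offset, the level ratio becomes 1/0.98³ = 1.062 after three falls by February, or 1/0.98⁴ = 1.084 if November is already 2% down. An offset of log days in the month returns 1.000.

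**The case against.** The strongest reply is that an offset is a coding detail usually left to the analysis plan, and that Poisson modelling of counts is the ordinary way to model rates. Objective 6 shares its follow-up with Objective 1 and is built on its results, and Table 11 names rates. All of this is true. A reader might infer that the protocol has decided against an offset; the documents do not say so. What stands is that section 8.8 specifies counts and a risk ratio where Table 11 specifies rates. Objective 1 produces both counts and rates, so pointing to it does not settle which is modelled.

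A reader might also infer that any movement in the denominator passes into the ratio, and cite section 11, which warns that "the denominators that will be used to calculate the incident use of drugs in the population may present an artefactual decrease". The documents do not support this. Steady drift is taken up by the trend; only a change near the intervention biases the estimate, and the protocol reports none. The section 11 artefact works the other way: it shrinks the denominator while new users remain, so it inflates rates and leaves counts alone. The offset would bring it in. The six-month exclusion exists to limit it.

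Three further limits on the size are fair:
- The German value comes from fitting a step and a slope to two points, which leaves no residual information after the intervention. That is a separate weakness, which an offset does not cure.
- The protocol allows seasonal terms and changes to the frequency of data points, either of which could reduce the artefact.
- Sampling error may hide it. At an assumed 100 new users a month, the 95% interval for the level ratio is about 0.73 to 1.15 in Germany and 0.82 to 1.13 in NAJS with 9 post months. At about 1,000 a month, the German interval is 0.85 to 0.98 and excludes 1. The protocol gives no monthly counts.

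**Conclusion.** The point holds as a contradiction with a computable consequence. If the 2022 model is fitted to raw counts as section 8.8 is worded, month length alone produces a false level drop of about 9% in Germany, 5% in Belgium and 3.5% in NAJS (6.5% if NAJS has only 3 post months). One annual seasonal pair reduces these to about 7%, 3% and 2% (5% for NAJS with 3 months). For the 2018 analysis the effect is about 1% and can be disregarded.

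These sizes assume the data locks in Table 3, a constant daily rate, a constant population, and a level contrast read at February 2023. Bias from a changing population at risk is possible, but its size cannot be derived from the protocol.

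This should be settled before the analytical code is written. It does not show that the Objective 6 result will be wrong, because the offset may still be intended and, with modest counts, the artefact would lie within the noise.

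**What to change.** Reconcile section 8.8 with Table 11 by stating that the Poisson or quasi-Poisson model includes the log of monthly person-time at risk from Objective 1 as an offset, and that the effect measure is an incidence rate ratio. Replace the term risk ratio in section 8.8 and Table 1 accordingly.

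Keep the exclusion of the last six months for the IQVIA sources, since the offset would otherwise carry the end-of-data denominator artefact into the estimate. In the same place, say whether the exclusion applies to NAJS. As a check, refit with log days in the month as the offset: a clear gap between the two fits would point to movement in the denominator.

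The cost is one sentence, the changed label and one extra model run. Objective 1 already produces the person-time.
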